7.1 Monitoring Schedule

Data will be collected at Screening, Baseline, Monthly Phone follow up, Quarterly visits, Withdrawal visit, Unscheduled visits, Participant withdrawal and at CAS closure and the detailed below. See Appendix 3 for a complete Monitoring Schedule.

7.2 Screening

The purpose of the screening visit is to determine patient eligibility. Completing the Participant Informed Consent process is required before initiating screening activities with the patient.

- Obtain and document consent from potential participant.
- Review medical history to determine eligibility based on inclusion/exclusion criteria.
- Review medications history to determine eligibility based on inclusion/exclusion criteria.
- Perform serum pregnancy test in females of reproductive age.
- Perform blood investigations to ensure meets eligibility criteria.

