4. DESIGN

4.1 Type

CAN-1 is a Compassionate Access Scheme designed to provide access to Epidiolex[®] to a maximum of 30 eligible paediatric patients (at any one time).

Epidiolex[®] will be prescribed by physicians endorsed by the TGA under the Authorised Prescriber scheme. Paediatric neurologists with an appointment at any QLD Public Health Organisation are invited by the CHQHHS Clinical Cannabis Project Office (PO) to submit an application to participate in CAN-1. The PO will assist the clinician where they meet the criteria prescribed in this protocol to obtain Authorised Prescriber status via the required application to their institutional HREC and then to the TGA.

Due to the limited supply of Epidiolex[®] at any given time, approval of an AP does not necessarily guarantee the inclusion of their patients in the CAS, but rather enables them to make application to the PO for consideration of eligibility. Further information concerning inclusion on the CAS is provided at Section 5.2.1 below.

Application to the PO will be made after the AP/Paediatric Neurologist contacts the patient and obtains verbal consent to release certain health information to the PO. This de-identified information, linked to the patient's file via unique identifier, will be used by the PO to rank the patient and determine suitability for inclusion in the CAS. Consent will be noted in the patient's file.

If the PO approves a request, the AP will be notified at which time they would schedule a screening visit with patient/parent. During this visit, the AP will review the Patient Information Sheet and Informed Consent Form (PISCF) with the patient/parent and address any questions. If the patient/parent voluntarily consents, the patient's eligibility will be reviewed, and if confirmed eligible, would be provided an initial prescription for up to 3 months of Epidiolex[®]. A site-based coordinator will be scheduled to facilitate during this enrolment process.

Upon review of a successfully completed informed consent form, the PO will provide the appropriate hospital pharmacy with the patient's unique identifier or authorization code, DOB and AP name. This information will also be present on the script. The pharmacy will only dispense the product once the unique identifier, DOB, and informed consent have been confirmed by the PO.

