5. PARTICIPANTS AND RECRUITMENT

5.1 Number of Participants

A maximum of thirty (30) patients may access this product at any given time. With replacements possible, the total sample size is unknown.

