5.2.2 Exclusion criteria

Patients who meet any of the following criteria are not eligible for participation:

- Pre-existing abnormalities of complete blood count, electrolytes, coagulation, hepatic function or enzymes that are considered clinically significant as judged by the Authorised Prescriber (e.g. WBC < 4, Platelets < 60000, ANC < 1.5, ALT or AST > 2 times upper limit of normal)
- Clinically significant ECG abnormalities (e.g. QTc > 460 msec, PR > 0.2 sec, QRS > 0.1 sec)
- Have a terminal illness, with life expectancy not longer than 3 months.
- Use of any cannabis-related product in the month prior to consent
- Female subjects who are pregnant will be excluded. Cannabidiol is contraindicated in pregnancy. If a female subject is able to become pregnant, she will require a negative serum pregnancy test before entry into the scheme. Female subjects will be informed not to become pregnant while taking cannabidiol. Female subjects must inform the investigator and consult an obstetrician or maternal-fetal specialist if they become pregnant during the study.
- Known allergy to CBD or any cannabinoid or any component of Epidiolex[®].

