7. CAS VISITS AND PROCEDURES

Once enrolled, participants are required to comply with monitoring requirements that take place both on a routine schedule and during unscheduled visits.

If under uncontrolled circumstances the participant is unable to perform a physical visit to the institution to complete a procedure outlined in the protocol (e.g. blood test), the institution can request a waiver and upon approval by the PO have the procedures completed at a local site. This does not mean that Epidiolex[®] can be dispensed at the local site. Epidiolex[®] can only be dispensed by an approved AP pharmacy and only by a pharmacist delegated to dispense Epidiolex[®].

The following data will be collected during monitoring:

- Seizure types
- Seizure Intensity or duration (week 4 onwards):
 - “Increased” (I) or “Decreased” (D) or No change (N)
- Body Weight
- Seizure Types
- Number of:
 - Days Rescue Medication was Used (in last 28 days)
 - Episodes of Status Epilepticus (SE) in the last 28 days, both convulsive and non-convulsive
 - Emergency Room (ER) visits in the last 28 days
 - Hospitalisations in the last 28 days
- Epidiolex[®] and Concomitant AEDs:
 - Dose
 - Plasma level (AED only)
- Biochemistry and Full Blood Count (FBC)
 - Na⁺
 - K⁺

- Cl-
- HCO₃
- BUN
- Creatinine
- RBC
- HCT
- HGB
- MCV
- MHC
- MCHC
- WBC and differential
- Platelets
- Liver Function Tests (LFT)
 - AST
 - ALT
 - Albumin
 - Total bilirubin
 - Gamma-glutamyl transferase (GGT)
 - Alkaline phosphatase (AP)
 - INR

For any clinically significant (> 3 x ULN) elevation of ALT or AST in patients being treated with Epidiolex[®], the following laboratory measures, at minimum, should be assessed within 72 hours: repeat ALT/AST, total bilirubin, alkaline phosphatase, and GGT.

All CAS participants with elevated LFTs should be followed until all abnormalities return to the baseline state as assessed by the AP with AST/ALT < 3X ULN. Please refer to section 7.8.1 for LFT abnormality criteria as a reason for withdrawal from the study.

- 24 hour Video EEG
- Serum Pregnancy Test (in all females of reproductive age)
- ECG
- Global Impression of Change (measured by patient/parent, and separately physician)
- Adverse Events
 - Diagnosis, syndrome, signs, symptoms
 - Severity
 - Plausible relationship to CAS medication
 - Action taken with CAS medication
 - Other action taken (if any)
 - Outcome
 - Serious adverse event (if yes, then reason for seriousness)
 - Start and Stop date

- Duration if <24hrs

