7.3 Baseline

Relevant information collected during the patient consent process and screening may be used in baseline monitoring, provided the patient completes all processes in the same visit. Female patients of child-bearing age will be subject to a serum pregnancy test. Patients who are pregnant will be excluded.

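### Section 7.8.2 sends withdrawing patients to the unscheduled visit (7.7) instead of the withdrawal visit (7.6), and the 7.2 screening list leaves out the ECG that a 5.2.2 exclusion needs (minor)

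*Protocol*

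**What the plan says.** **Withdrawal.** Section 7.6 (Withdrawal visit) requires FBC, EUC, LFT, AED plasma levels and an ECG when a patient withdraws, and has the reason for withdrawal recorded. Section 7.7 (Unscheduled visit) sets a minimum of weight and height, FBC, EUC, LFT and AED plasma levels, and asks for the reason for the visit. Section 7.8.2, on handling withdrawals, says that final monitoring follows Section 7.7.

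**Screening.** One exclusion in Section 5.2.2 reads "Clinically significant ECG abnormalities (e.g. QTc > 460 msec, PR > 0.2 sec, QRS > 0.1 sec" (closing bracket omitted). Section 7.2 gives the screening visit the purpose of establishing eligibility. It lists consent, review of medical history, review of medication history, a serum pregnancy test where applicable, and finally "Perform blood investigations to ensure meets eligibility criteria". No ECG is listed. Section 7.3 (Baseline) names only a pregnancy test, and says that screening information "may be used in baseline monitoring, provided the patient completes all processes in the same visit".

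**Where else the ECG appears.** The general list in Section 7, introduced by "The following data will be collected during monitoring", includes an ECG but ties it to no visit. Section 7.1 names Screening and Baseline among the data collection points and adds "See Appendix 3 for a complete Monitoring Schedule". Appendix 3 is not among the pages at hand.

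**The concern.** The stated objective of the scheme is provision of the product and safety monitoring, so the visit procedures carry most of the weight that a design and analysis section would carry in a trial.

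On withdrawal, two sections give different instructions for the same event. A coordinator who follows 7.8.2 literally completes the unscheduled-visit minimum and takes no exit ECG. That would include a child withdrawn under 7.8.1 because an ECG abnormality listed among the exclusions had developed.

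On screening, the ECG exclusion is worded in terms of intervals that are read from a tracing. Under Section 4.1 the patient's eligibility is reviewed after consent at the screening visit and, "if confirmed eligible, would be provided an initial prescription for up to 3 months". If the list that guides that visit does not prompt for an ECG, the criterion may be applied unevenly between prescribers, or applied on history alone.

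**Working it through.** No arithmetic beyond counting applies, and the protocol states no figure on this point to reproduce. The check sets the sections side by side.

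**1. Withdrawal visit against the section that 7.8.2 cites**

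| Item | 7.6 Withdrawal visit | 7.7 Unscheduled visit (minimum) |
|---|---|---|
| FBC | yes | yes |
| EUC | yes | yes |
| LFT | yes | yes |
| AED plasma levels | yes | yes |
| ECG | yes | no |
| Reason for withdrawal | yes | no (reason for the visit only) |
| Weight and height | no | yes |

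The 7.7 minimum contains four of the five assessments in 7.6 (5 − 1 = 4). The missing assessment is the ECG, and the reason for withdrawal is not asked for either. The section titles leave no doubt about which one was meant. This result does not depend on Appendix 3, because both sections and the reference are in the body text.

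**2. Exclusions against the screening list**

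Section 5.2.2 has six exclusion criteria: laboratory abnormalities, ECG abnormalities, terminal illness, recent cannabis use, pregnancy and known allergy. Three of the six depend on a test result.

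| Test-based exclusion (5.2.2) | Test listed in 7.2 | Test named in 7.3 |
|---|---|---|
| Blood count, electrolytes, coagulation, hepatic function | yes | no |
| ECG (QTc, PR, QRS) | no | no |
| Pregnancy | yes | yes |

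Section 7.2 therefore lists two of the three tests. It does not leave all eligibility tests to the appendix or to the history review, since it names the other two itself.

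**3. Does another section place an ECG before the first dose?**

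The Section 7 list does not settle it. It cannot apply in full at every contact, because it also holds a 24 hour video EEG and Section 7.4 allows the monthly contacts to be by phone. Table 9.1 gives non-laboratory data a screening time point but does not name the ECG. Appendix 3 could settle it, but is not shown.

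**4. How many children**

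This cannot be derived. For the screening gap, the number without a pre-dose ECG is none if Appendix 3 schedules one or the prescribers order one to apply 5.2.2. If neither holds, it is at most every enrolled child. Section 5.1 says "A maximum of thirty (30) patients may access this product at any given time", and with replacements the total is unknown. The number of withdrawals is not stated either.

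**The case against.** The strongest reply is that both rules bind on their own terms. Section 5.2.2 is an exclusion whatever 7.2 lists, and a prescriber cannot properly rule out a prolonged QTc without a tracing. The history review in 7.2 is directed at the inclusion and exclusion criteria and could draw on an existing ECG. Section 7.6 applies whenever a patient withdraws, a wrong pointer elsewhere does not cancel it, the 7.7 set is only a minimum, and Appendix 6 is a dedicated withdrawal form. The visit sections are also plainly not exhaustive: 7.5 lists no procedures for the quarterly visit, so silence in them is weak evidence that something is not done. All of this stands, and it keeps the point minor. It does not remove the conflict between 7.8.2 and 7.6, or the fact that 7.2 lists two eligibility tests and omits the third.

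Three stronger readings are tempting and are not supported.

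- *Children start treatment without an ECG.* Appendix 3 may schedule one, so the documents at hand cannot show this.
- *The release step lets an unscreened child through.* Section 4.1 does say "The pharmacy will only dispense the product once the unique identifier, DOB, and informed consent have been confirmed by the PO", but that check includes no test result at all, bloods and pregnancy included. It shows nothing specific to the ECG.
- *Without a pre-dose tracing the prescriber cannot tell a new abnormality from an old one, so the withdrawal rule fails.* A clinically significant abnormality bars the child at entry under 5.2.2 and requires withdrawal if it develops under 7.8.1. The action hardly depends on which it is.

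**Conclusion.** The point holds in a limited form, at minor severity.

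The reference in 7.8.2 is wrong as written. It sits in operative text and conflicts with 7.6 on the ECG and on recording the reason for withdrawal. This rests on the body text alone.

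The 7.2 list is inconsistent with 5.2.2, because it covers two of the three tests that the exclusions need. Whether any child actually goes without a pre-dose ECG depends on Appendix 3 and on prescriber practice, neither of which can be seen. No statistical figure is affected.

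**What to change.** - In 7.8.2, change the reference from Section 7.7 to Section 7.6.
- In 7.2, add a bullet: *Perform an ECG, reviewed by the AP against 5.2.2 before the first prescription.*
- Let that tracing serve as the baseline ECG. Section 7.3 already allows this when everything is completed in one visit; add a phrase so that it also counts when screening and baseline fall on separate days.
- Confirm that Appendix 3 agrees with these changes.

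The edit is one section number, one bullet and one phrase. ECG is already a scheme procedure in Section 7. The downside is at most one extra ECG per screened child, none if Appendix 3 already schedules it, and possibly a short delay to the first prescription.

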7.3 Baseline

Relevant information collected during the patient consent process and screening may be used in baseline monitoring, provided the patient completes all processes in the same visit. Female patients of child-bearing age will be subject to a serum pregnancy test. Patients who are pregnant will be excluded.

7.4 Monthly Phone Follow-up

Monitoring activities may be conducted via phone at 4 weeks and 8 weeks after the baseline, or quarterly in-person visits. A study coordinator will make the calls and record the relevant information. Section 9, Data Management, describes the recording and management requirements for this information.

7.5 Quarterly visit

The AP will schedule quarterly visits with the patients and invite the project office staff to participate. The first visit will be 3 months (+/- 2 week window) from baseline.

7.6 Withdrawal visit

A patient may withdraw at any time. In this case the patient will be assessed for FBC, EUC, LFT, AED plasma levels, and ECG. Reason for withdrawal will be recorded. CBD is recommended to be tapered at 10%/day until completely off of drug.

7.7 Unscheduled visit

The AP is required to notify the project office if there is an unscheduled visit. Details of the reason for the visit, any adverse events, and blood tests would need to be documented and forwarded to the project office. If the visit is due to an Adverse Event or a Serious Adverse Event, then all procedures described in Section 8, Adverse Events and Risks, will be followed.

At a minimum, weight & height, FBC, EUC, LFT, AED plasma levels will be measured and recorded.

7.8 Participant Withdrawal

7.8.1 Reasons for withdrawal

Patients are free to withdraw from the study at any time upon their request or the request of their legally acceptable representative. Withdrawing from the study will not affect their access to standard treatment or their relationship with the hospital and affiliated health care professionals.

The patient must be withdrawn from the CAS if any of the following events occur:

- The patient experiences an Adverse Event or Serious Adverse Event which in the opinion of the AP would compromise the continued safe participation of the patient in the CAS
- Develops, during the course of the study, symptoms or conditions listed in the exclusion criteria
- The patient becomes pregnant, as evidenced via a positive pregnancy test
- The patient is unwilling or unable to continue, or the parent/legal representative is unwilling or unable to allow the patient to continue
- The AP decides that withdrawal is in the patient's best interests
- ALT or AST >8xULN
- ALT or AST >5xULN for more than 2 weeks
- ALT or AST >3xULN and (TBL >2xULN or INR >1.5)
- ALT or AST >3xULN with the appearance of fatigue, nausea, vomiting, right upper quadrant pain or tenderness, fever, rash, and/or eosinophilia (>5%)

All patients with elevated LFTs should be followed until all abnormalities return to the baseline state as assessed by the investigator with AST/ALT < 3X ULN.

The Authorised Prescriber may withdraw a patient from the CAS if the patient:

- Does not fulfil the monitoring requirements
- Shows an increase, or no measureable improvement, in seizure frequency and/or severity as assessed by the AP.

The Authorised Prescriber will also withdraw all participants if the CAS is terminated either

due to Epidiolex[®] being registered by the TGA, or in the event GW Pharmaceuticals ceases to supply product.

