8.2 Assessment and documentation of adverse events

For the purposes of the CAS the Authorised Prescriber is responsible for the recording of all Adverse Events, regardless of their relationship to study drug, with the following exceptions:

- Conditions that are present at screening and do not deteriorate will not be considered adverse events.
- Abnormal laboratory values will not be considered adverse events unless deemed clinically significant by the investigator and documented as such.

AEs will be reviewed for each patient at their scheduled visit and during unscheduled visits including phone calls from patients/parents and relevant health professionals. During the visit the AP or Study Coordinator will collect the following information from the patient:

The description of each AE will include:

- A description of the AE (Diagnosis of Syndrome only [if known] or signs/symptoms);
- The date started, stopped, as well as duration if <24hrs;
- Epidiolex® total Daily Dose at Time of Event;
- Outcome (recovered, recovered with sequelae, continuing, death);
- Severity (mild, moderate or severe);
- Plausible relationship to medication (Yes/No);
- Any action taken, (e.g. treatment, follow-up tests);
- Is it an SAE? If yes, reason.

Where required information is unavailable during the visit, a follow-up will be made by the AP as soon as practicable to complete the AE record.

If the AE is determined to be an SAE, then the AP will inform the relevant parties as per Table 8.4 Serious Adverse Event Reporting including within the specified timeframes and reporting formats.

The AP or study coordinator will record all AEs in WebSpirit in real-time, or transcribed from hardcopy (see Appendix 3) on a monthly basis, as described in Section 9.1.2. If transcribed from hardcopy, then the hardcopy source documentation is kept in the patient's file.

An AP according to the definition in section 8.1 will assess the seriousness of an AE.

For ongoing fluctuations in the severity of an AE, the most severe assessment should be documented. AEs characterised as intermittent will be documented for each episode. All AEs will be followed to adequate resolution, where possible.

Causality assessment is required for all AEs and SAEs. Causality assessment must only be

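### Section 7.8.1 carries the exclusion criteria into mandatory withdrawal without saying how that bullet relates to the graded liver rules, so an isolated ALT/AST above 3xULN can have opposite outcomes

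*Protocol*

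**What the plan says.** All from the protocol.

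- **Section 7.8.1** opens its list with "The patient must be withdrawn from the CAS if any of the following events occur". One entry covers a patient who "Develops, during the course of the study, symptoms or conditions listed in the exclusion criteria".
- **The same list** has four graded liver entries: "ALT or AST >8xULN"; "ALT or AST >5xULN for more than 2 weeks"; above 3xULN with total bilirubin above 2xULN or INR above 1.5; and above 3xULN with listed symptoms or eosinophilia.
- **Section 5.2.2** excludes abnormalities of "hepatic function or enzymes that are considered clinically significant as judged by the Authorised Prescriber". Its bracketed examples include "ALT or AST > 2 times upper limit of normal".
- **Section 7** begins its on-treatment instruction with "For any clinically significant (> 3 x ULN) elevation of ALT or AST in patients being treated with Epidiolex". It then asks for at least a repeat ALT/AST, total bilirubin, alkaline phosphatase and GGT within 72 hours. Elevated tests are to be followed back to baseline state with AST/ALT below 3xULN, and the reader is sent to 7.8.1 for the liver criteria for withdrawal.

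Section 7.8.1 neither exempts liver enzymes from the exclusion-criteria entry nor ranks its entries.

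**The concern.** A graded scheme with durations and accompanying conditions makes sense only if isolated elevations below those levels can be tolerated for a time. The exclusion-criteria entry, in the same mandatory list, appears to remove that tolerance. Two prescribers with the same laboratory result, each following the text, could reach opposite mandatory outcomes.

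This matters in two ways. For the child, withdrawal means stopping the product; Section 7.8.2 itself raises a general concern about seizure deterioration when an anticonvulsant is stopped abruptly, and under 7.8.3 the place goes to the next patient in line. For the data, safety monitoring is the scheme's stated outcome, and Section 3 gives evaluation of safety in an Australian population as a secondary purpose. Withdrawals for liver findings and time on treatment would then partly reflect which entry a prescriber followed.

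**Working it through.** There is no sample size, power or error rate to recompute, and the plan states no figure on this point. The check sets the rules side by side over ranges of ALT/AST.

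**Step 1. Does the exclusion-criteria entry reach on-treatment values?** Section 5.2.2 is worded for pre-existing abnormalities. The 7.8.1 entry expressly covers what develops during the study, so it moves the listed conditions onto treatment.

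**Step 2. What makes an enzyme elevation a listed condition?** The test in 5.2.2 is clinical significance in the prescriber's judgement. The figure of 2xULN is an example of it and not a cut-off.

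**Step 3. Does the protocol say when an on-treatment elevation is clinically significant?** Yes. Section 7 attaches that label to values above 3xULN.

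**Step 4. Compare the rules.** Take an isolated elevation: no listed symptoms, no eosinophilia, bilirubin and INR normal.

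| ALT/AST | Exclusion-criteria entry | Graded liver entries | Section 7 |
|---|---|---|---|
| >2x to 3xULN | Withdraw only if the prescriber judges it significant, for instance by applying the 5.2.2 example | No withdrawal | Not labelled clinically significant |
| >3x to 5xULN | Withdraw, if Section 7's label is applied | No withdrawal | Repeat panel within 72 hours, follow-up |
| >5x to 8xULN, 2 weeks or less | Withdraw, if Section 7's label is applied | Not yet | Repeat panel within 72 hours, follow-up |
| >5x to 8xULN, more than 2 weeks | Withdraw, if Section 7's label is applied | Withdraw | Sends the reader to 7.8.1 |
| >8xULN | Withdraw, if Section 7's label is applied | Withdraw | Sends the reader to 7.8.1 |

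**Step 5. Two worked cases.**

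- *Isolated 4xULN.* 4 > 3, so Section 7 calls it clinically significant and the exclusion-criteria entry applies. It is not above 5x or 8x and has no accompanying finding, so no graded entry is met.
- *Isolated 6xULN for under two weeks.* 6 > 3, so the exclusion-criteria entry applies at once. It is above 5x, but the duration condition is not met, and 6 < 8. The two-week allowance has no effect if the first entry has already applied.

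The rules therefore disagree in rows two and three, and in row one only through the prescriber's judgement.

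**The case against.** The strongest reply is that 5.2.2 turns on the prescriber's judgement. On that view 7.8.1 combines a discretionary entry with fixed limits, which is a coherent design: the list has other judgement entries, and overlap between entries joined by *any* is not in itself a contradiction. One can add that 5.2.2 speaks of pre-existing abnormalities, and that Section 7's pointer to 7.8.1 most naturally means the explicit ALT/AST entries.

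Much of this stands, and it rules out two stronger readings. A reader might infer that 2.5xULN automatically forces withdrawal; it does not, because 2xULN is only an example subject to judgement. A reader might also infer that the graded entries could never be the first to apply. That goes too far: where the prescriber does not judge an elevation significant, they act as fixed limits.

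The reply is weaker above 3xULN. There the protocol itself supplies the words clinically significant, so a prescriber who declines to apply the exclusion-criteria entry must set aside Section 7's label. The pre-existing wording does not help, given the reference to what develops during the study. Section 7's pointer leads to a list that contains both kinds of entry.

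**Conclusion.** The text is wrong as written, in a limited range. For isolated ALT/AST above 3xULN and up to 8xULN, excluding values above 5xULN for more than two weeks, one entry in 7.8.1 calls for mandatory withdrawal while the graded entries do not, and Section 7 asks for retesting and follow-up. This assumes that clinically significant means the same in Section 7 as in 5.2.2. Between 2x and 3xULN the conflict depends on the prescriber applying the example.

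Three further inferences are not supported:

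- *Adverse event recording.* Section 8.2 says "Abnormal laboratory values will not be considered adverse events unless deemed clinically significant by the investigator and documented as such". That rests on the investigator's judgement, has no numeric threshold and refers to neither 5.2.2 nor Section 7, so no distortion of hepatic adverse event counts is shown.
- *Blood count and ECG examples in 5.2.2.* The same entry brings these onto treatment, but no competing on-treatment rule exists for them, so they add no contradiction.
- *A count of affected children.* The protocol gives no frequency of such elevations. Thirty is the maximum at any one time, and Section 5.1 says the total is unknown.

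I would rate this below must-fix. The scheme defines no research question and lists one site. The point still bears on patient safety and is cheap to settle.

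**What to change.** Reconcile Sections 5.2.2, 7 and 7.8.1. State in 7.8.1 either that the exclusion-criteria entry applies to on-treatment ALT/AST, or that the graded liver entries alone govern it. Then align the use of clinically significant for on-treatment ALT/AST with that choice. Which rule applies is for the sponsor's clinical team, and this review proposes none.

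The cost is one sentence in 7.8.1 and one matching definition, with no new data or visits. Because the change touches patient safety, Section 11.1 would treat it as an amendment needing approval from the ethics committee and the manufacturer.
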